6 STUDY INTERVENTION

6.1 STUDY INTERVENTION(S) ADMINISTRATION

6.1.1 STUDY INTERVENTION DESCRIPTION

NewbornDx and rWGS are CLIA/CAP certified and will be completed for all infants. The Athena (Quest) and RCIGM laboratories will be blinded to each other's result until all final results are returned.

Phenotype Extraction and Provision of Clinical Information to the Laboratories

1. A sub-group of clinicians from each site will manually review the medical record, extract relevant clinical information and determine the Human Phenotype Ontology (HPO) terms (refer to MOP). The sub-group of clinicians will consist of a minimum of 3 clinicians with at least one a geneticist or genetic counselor.
2. A small portion of the medical records (genetics consult note, other sub-specialty note (neurology, hematology, etc.) and NICU notes will be selected.
3. The HPO terms and medical records will be provided by the sites to the laboratories via upload to the RCIGM ordering portal. Athena will receive this data to its systems through a secure FTP site or encrypted email. Athena will not have access to the rWGS results through this mechanism.
4. Once HPO terms are submitted by the site, the laboratories may either add additional terms based on the last consult/progress notes submitted by the site or contact the site research team for clarification of symptoms. If this happens by either Athena (Quest) or RCIGM, the additional or revised HPO terms needs to be redirected to the site for upload to the portal. This ensures any new information is shared with both laboratories.

Athena Diagnostics (Quest)

NewbornDx Methods and Workflow

Rapid NewbornDx will be performed at Athena (Quest) Diagnostics to CLIA/CAP requirements. DBS will be collected on filter paper and sequenced. Custom oligonucleotide probe libraries (Agilent SureSelectQXT) will be utilized to capture genomic DNA regions and targeted libraries created as described earlier⁴². The content of the assay (regions of interest) will remain constant for participants in the study. Sequencing of the targeted libraries will be performed on a NextSeq 500 (Illumina, San Diego, CA). Sequencing reads will be aligned to the reference genome (hg19/GRCH build 37) using Burrows-Wheeler Aligner for short alignments (BWA-MEM) followed by a Genome Analysis Toolkit v3.6 (GATK) haplotype variant caller running on the Edico Dragen™ Platform, and annotated with Enterprise genome interpretation software (Fabric Genomics, Oakland, CA). All subject FASTQ, Variant Call File (VCF) and other data files will be securely stored within the Athena (Quest) Diagnostics Isilon storage.

Athena (Quest) Genomic Data Analysis

Data analysis will be completed by a custom bioinformatics pipeline utilizing Burrows-Wheeler Aligner & Genome Analysis Toolkit v3.6. All reported DNA variants will be reviewed by at least one trained genomic variant scientist, one genomic science specialist, and one board-certified laboratory director prior to the final report being issued.

Athena (Quest) Variant Pathogenicity Determination

Variant pathogenicity is assessed following a standardized evaluation protocol⁷¹ consistent with the ACMG standards and guidelines for the interpretation of sequence variants⁴⁹. Data is gathered from multiple sources, including but not limited to, internal datasets, published literature, public databases, and in-silico prediction tools. Evidence is reviewed and assessed by a genomic variant scientist using a standard operation procedure. The proposed pathogenicity classifications derived from the data are reviewed and approved by a board-certified laboratory director.

Athena (Quest) Variant Causality Determination

Variant causality will be determined by the infant's clinical presentation, family history, and any other laboratory results provided. Relevant HPO terms (see phenotype extraction above) will be used with Phenomizer or Phenolyzer to create a differential diagnosis based on the neonate's clinical presentation. Phevor (Fabric Genomics) will be used to prioritize DNA variants based on the genes' associated phenotypes compared to the HPO terms provided by the site. Fabric Genomics will also be used to filter variants based on variables such as inheritance pattern, frequency of the DNA variant in the general population, variant type (missense, nonsense, etc.), and presence in a variant database (i.e. ClinVar or HGMD). Variant filtering will be based on a standardized set of criteria used by genomic variant scientists and board-certified laboratory directors. Sample reports will be drafted and reviewed by a team composed of genomic variant scientists, genetic counselors, and a board-certified director prior to being released to the client.

RCIGM-CGC

rWGS Methods and Workflow

rWGS will be performed at the CLIA-certified, CAP accredited Rady Children's Institute for Genomic Medicine – Clinical Genome Center (RCIGM-CGC). Sequencing is performed in accordance with the RCIGM- CGC standard operating procedures and validations. Briefly, genomic DNA is extracted from whole blood, PCR-free DNA libraries are made, and quality checks performed for library size and concentration. DNA libraries are then loaded on a NovaSeq 6000, and 2 x 100 nt sequencing to an average genome wide coverage of 40x. Short Tandem Repeat (STR) genotypes will be used to assure sample identity is maintained throughout the laboratory process. For each infant or biological parent sample, STR genotypes are generated by a commercial PCR amplification kit and are compared with those called by WGS process. Bcl files are automatically aligned to hg19/GRCH build 37 and nucleotide variants and small insertions and deletions are called with DRAGEN (Edico Genome) in ~1 hour. Files are uploaded to DNAexus, where structural variants (SVs) are called using the union of

two algorithms (CNVnator and Manta). Redundant SVs are removed from the superset of SV calls. SVs will be annotated to determine affected genes and regulatory regions and compared to public and internal databases to determine MAF and filter common, or false positive SVs. A combined VCF (SNVs/indels and SVs) are uploaded to a rapid instance of Opal (Fabric Genomics), allowing annotation and display within 1 hour.

rWGS Trio Testing

When samples for the infant and parent(s) are received at the same time, RCIGM will generate infant and parent sequences simultaneously and the data from the infant and parent(s) will be analyzed together as a duo/trio. When infant samples are sent without the parent samples, RCIGM will sequence the infant sample and analyze the infant's data. If a diagnosis is not determined or a VUS is identified after analyzing the infant alone, the parents' samples, if subsequently become available, will be sequenced and data from the duo or trio analyzed together. The infant's report of results will indicate whether or not trio testing was done. For all positive diagnoses made when only sequencing and analyzing the infant, the lab will subsequently run testing on the parent samples (if available) to determine inheritance (for example, targeted Sanger sequencing).

RCIGM-CGC Genomic Data Analysis

Data analysis will follow the standards set by the clinical diagnostic laboratory and in accordance with recommendations from the American College of Medical Genetics and Genomics (ACMG/AMP). A minimum of two expert data analysts will be responsible for analyzing the DNA variants following genomic sequencing. Analysts will be rotated among qualified staff, including but not limited to laboratory directors, genetic counseling staff, and trained medical and research staff. One of the analysts will then compile a report to be reviewed and reported by an ABMGG board-certified laboratory director.

RCIGM-CGC Variant Pathogenicity Determination

The laboratory directors as well as Medical Geneticists and Genetic Counselors at RCIGM and at each site will assess pathogenicity of variants according to ACMG/AMP recommendations for classifying sequence. New statistical approaches for variant classification are currently being actively developed by several groups and may be introduced upon verification of their utility. Knowledge of the pathogenicity of individual SNVs and SVs is rapidly evolving through community curation via HGMD, ClinVar and DECIPHER50 and through exhaustive mutant generation and functional testing for individual disorder genes. Variant classification will be performed using expert analysis of all data regarding each variant, including review of available literature and functional models.

RCIGM-CGC Variant Causality Determination:

Variant causality will be determined on a case by case basis depending on the infant's clinical presentation, family history, and any other laboratory results provided. Relevant HPO terms will be used with software tools, such as Phenomizer or Phenolyzer or standard gene lists for common presentations (e.g. neonatal seizures, cholestasis, and

heterotaxy), to create a differential diagnosis list based on the neonate's clinical presentation. Inputs for causality determination will be the annotated genomic variant file and the comprehensive differential diagnosis gene list. Alternatively, the Phevor tool in Opal^{52, 53} will be used to rank genes with relationship to the observed phenotype based on their known or suspected association(s). By allowing dynamic filtering of variants based on variables such as individual clinical features, disorders, genes, genotype, and inheritance pattern, Opal will assist in identification of a molecular differential diagnosis. Custom Opal settings can be saved, which allows configuration in a manner that can enable a provisional diagnosis to be determined rapidly. Opal also allows data mark-up, user tracking and data basing of variants and their classifications and export of fields in formats suitable for inclusion in diagnostic reports. In a typical interpretation session, variants will be filtered by allele frequency and presence in variant databases and prioritized based on phase, parent-of-origin, clinical features, and other characteristics unique to the infant or to the biological parents. All potential genetic inheritance patterns will be examined, including de novo, autosomal recessive, autosomal dominant, X-linked, mitochondrial, and, where possible, somatic variation (where trios may be needed). Where a single likely causative heterozygous variant for a recessive disorder is identified, the entire coding domain will be manually inspected using the Integrated Genome Viewer (IGV) for coverage and to screen for additional variants that may not have been called. Expert interpretation will be performed for all likely causative variants with regard to evidence for pathogenicity and causality. Likewise, the causality of structural variants in rWGS is assessed based on frequency in the RCIGM-CGC database and location with respect to the comprehensive differential diagnosis gene list⁵⁴. This is an evolving area of interpretation. SV and nucleotide variant causality is examined together in order to identify compound heterozygosity in recessive disorders.

Secondary/Incidental Findings for the Infant

Secondary/incidental findings for an infant will not be actively sought. A dedicated analysis of the ACMG 59 secondary gene list will not be done. If a secondary/incidental finding is found during the infant analysis, the laboratory will only report it if both criteria 1 and 2 are met and either 3a or 3b:

1. The parent/guardian opted to receive secondary findings for the infant, AND
2. The disorder onset may occur in childhood, AND
3. At least one of the following:
 - a) The disorder is medically actionable AND/OR
 - b) The disorder involves a gene on the "American College of Medical Genetics and Genomics (ACMG) list" of genes recommended for reporting of secondary findings at the time of testing

Secondary findings of conditions with an onset only in adulthood will not be returned for the infant. Only pathogenic or likely pathogenic variants are reported as a secondary/incidental finding if they have the potential to impact the infant during childhood.

The "ACMG list" refers to the current list of genes recommended to report as secondary findings. WGS covers all 59 genes currently recommended by the ACMG to return as

secondary findings, NewbornDx covers 30 of those genes. There are 52 genes on the ACMG list that may occur in childhood. In order to account for how the ACMG list might evolve during the study period, the ACMG list at the time testing is done will be used. Therefore, the list used for the first infant enrolled may be different than the list used for the last infant enrolled. If the ACMG list evolves during the study period, we will not retrospectively change what was initially reported; this aligns with current clinical practice.

Primary and secondary findings for the infant, if reportable, will be included in one report from each laboratory.

Secondary Findings for a Biological Parent

A secondary finding for a biological parent may be identified through WGS when conducting the infant's phenotypically driven analysis. Secondary findings for a parent will not be actively sought and a dedicated analysis of the ACMG 59 secondary gene list will not be done. There may be cases in which a biological parent elects to receive secondary findings and the parent's sample does not undergo WGS. This could occur if the infant's samples have been processed prior to the receipt of the parent samples. Secondary findings for a biological parent will not be reported by Athena Diagnostics.

The laboratory will only report a secondary diagnosis for a biological parent if all of the following criteria are met:

1. The biological parent opted in to receive secondary findings for him or herself. A parent may opt-in to receive secondary findings only if the parent/guardian opted-in for infant secondary findings.
2. The disorder is of a gene on the ACMG list of genes recommended to report as secondary findings at the time of testing.

A separate report must be issued for any secondary findings for a biological parent.

When Incidental/Secondary Findings Are Reported

Secondary/Incidental finding found in Infant and Parent	Did Infant Opt-In?	Report for Infant?	Did Parent Opt-in?	Report for Parent?
Included in ACMG59, adult onset	Yes	No	Yes	Yes, RCIGM*
Included in ACMG59, adult onset	Yes	No	No	No
Included in ACMG59, adult onset	No	No	No	No
Included in ACMG59, childhood onset	Yes	Yes	Yes	Yes, RCIGM*
Included in ACMG59, childhood onset	Yes	Yes	No	No
Included in ACMG59, childhood onset	No	No	No	No
Not on ACMG59, childhood onset, medically actionable	Yes	Yes	Yes	No
Not on ACMG59, childhood onset, medically actionable	Yes	Yes	No	No
Not on ACMG59, childhood onset, medically actionable	No	No	No	No

*Athena/Quest will not report secondary/incidental findings for parents.

Confirmatory Testing

With the exception of a provisional result, pathogenic and likely pathogenic variants (as determined by ACMG variant classification criteria) that relate to the neonate's current phenotype as well as suspicious VUS will be clinically confirmed at RCIGM or Athena prior to the return of written results. Additional confirmation testing may be done by Sema4 for subjects enrolled at Mount Sinai (refer to Sema4 section below). Segregation analysis on biological parents will be performed when warranted. A provisional result will be given in cases in which delaying the return of results until confirmatory testing occurs places the infant at an increased risk of morbidity or mortality (a treatment modality is available whose delay in administration could cause irreversible harm). Prior to confirmation testing, the laboratory will return provisional results and management guidance via verbal report with read back followed by a written provisional result report to the enrolling site. Refer to the section, Sema4 and Subjects Enrolled at Mount Sinai, for when provisional results may be given for subjects from Mount Sinai.

Confirmatory testing will subsequently be performed for all provisional results and a written report of the final result issued. The laboratory will make the decision about whether a finding meets the criteria to be given provisionally; if there is a question, the lab will consult with the study-wide PIs. A lethal condition will not be released as a provisional result; it will be confirmed prior to this result reported.

Variant Classification	Is confirmation testing needed?
Pathogenic	Yes
Likely Pathogenic	Yes
Variant of Unknown Significance (VUS)	Only if suspicious (where the phenotypic fit is very good and/or functional confirmatory tests are readily available and/or the results are actionable)
Likely Benign	No
Benign	No

Secondary diagnoses	Is confirmation testing needed?
A secondary or incidental finding that will be reported	Yes

Category	Definition	Detected By NewbornDx	Detected by rWGS	Method(s)
SNP	variation in a single nucleotide	Yes	Yes	Confirmation testing methods are at the discretion of the laboratory director.
Indel	an insertion or deletion of less than 1 kb in length, in-frame and frame shift	Yes	Yes	Common methods include MLPA, microarray, Sanger and qPCR.
Structural Variant	Inversions, balanced translocations, CNVs; ~ 1 kb and larger	No	Yes	

Sema4 and Subjects Enrolled at Mount Sinai

Results returned to the medical record for subjects from Mount Sinai must be from a New York State CLIA certified lab and of a New York State conditionally approved test. Athena Diagnostics is a New York State CLIA certified lab and NewbornDx is a New York State conditionally approved test. Therefore, NewbornDx results for subjects from Mount Sinai will be returned to the research team, clinician(s) caring for the subject, the subject's parent/guardian(s) and placed in the subjects' medical record. Provisional results from NewbornDx may be acted upon prior to Athena's own confirmation testing.

Until the time RCIGM becomes a New York State CLIA certified laboratory and rWGS a New York State conditionally approved or approved test, subjects from Mount Sinai may require additional confirmation testing by Sema4. Sema4 is a New York State CLIA certified and Mount Sinai wholly owned laboratory. Procedures to be followed:

1. The research team at Mount Sinai will send samples to Sema4. Sema4 will extract DNA from the infant and biological parent blood samples and send two aliquots to RCIGM-CGC while retaining an aliquot for possible future confirmation testing. DNA requirements: > 3 ug DNA (concentration ranges from 20 ng/ul to 200 ng/ul) with Picogreen measurement. If the site used non-Picogreen measurement, 4-5 ug DNA (concentration ranges from 20-200 ng/ul).
2. RCIGM will issue a research grade report of its results to the research team at Mount Sinai. This report will have the heading "research report" and also include disclaimers in the Regulatory Disclosures section. The research report will only be placed in the research file and not in the medical record.
3. A provisional result will be given to the research team in order for them to alert Sema4 to start confirmation testing if required (i.e. RCIGM reports a provisional result which is not also reported by Athena). A RCIGM provisional result will not be shared with the clinical team, parent/guardian nor put in the medical record.
4. Pathogenic, likely pathogenic or VUS results returned only by RCIGM will have additional confirmation testing and interpretation done at the Sema4 laboratory. If RCIGM and Athena report the same result, Sema4 confirmation testing is not required. At Sema4, confirmation testing will be done by targeted analysis with Sanger, or for CNVs with qPCR, MLPA, or ultra-high resolution exon array.
5. RCIGM will send final results as a research report to the Mount Sinai research team. The Mount Sinai research team will compare the RCIGM research report with Athena's report and alert Sema4 of confirmation testing as necessary.

RCIGM Result	Agreement with NewbornDx	Is testing by Sema4 required?	What reports are put in the medical record?
Pathogenic, likely pathogenic, VUS or secondary/ incidental result	The findings reported by RCIGM are also reported and interpreted within the similar variant classification categories (P/LP v. VUS) by Quest/Athena.	No	NewbornDx
	RCIGM reports findings that Quest/Athena did not report.	Yes	NewbornDx, Sema4
Negative Result	Yes	No	NewbornDx
	No	No	NewbornDx

If during the course of this study, the RCIGM rWGS test becomes CLIA certified in New York State and the rWGS test is New York State approved or conditionally approved, the processes involving Sema4 will be eliminated.

Discordant Results

It is possible that the final results of NewbornDx and rWGS may be discordant. It is also possible that the confirmatory testing done by Sema4 for infants enrolled at Mount Sinai will be discordant to the confirmed NewbornDx or rWGS results. This could be a result of both technical and interpretation differences:

- technical differences of the platforms where a specific variant may be identified on one platform but not another
- different genotyping and variant filter thresholds when both platforms return the same variant
- different classification of the same variant as benign, likely benign, VUS, likely pathogenic or pathogenic

Which methods are used for confirmation testing at each laboratory will be documented.

It will be determined if the discordance is caused by the technical performance of the platform or variant filtering or classification. In cases of discordance due to variant classification, each lab will use an agreed upon format to provide a written document summarizing the evidence supporting their variant classification. Refer to section 8.1 and the MOP for adjudication procedures.

Inconclusive Results

Under certain circumstances, a test result may not be conclusive. These situations will be reviewed on an individual basis and testing may be repeated or another sample requested. The reasons for inconclusive testing are explained in the result report.

Requests for Re-analysis of Sequencing Data

Requests for reanalysis can only be made after a significant change in phenotype occurs in the infant (e.g. new onset seizures) when results have already been returned. This may be permitted on a case-by-case basis only after discussion between the enrolling site PI and study-wide PIs.

Retrospective Singleton (Proband) Analyses for Duo/Trios

After the final result is returned for an infant using a duo or trio analysis, Athena analysts will conduct a retrospective analysis of only the infant's NewbornDx data. The purpose of this analysis is to determine if the same result obtained with a duo/trio could have been obtained with only the infant's sample. The analysts who conduct the retrospective analysis will not know the result that was returned for the subject. The retrospective infant-only analyses will occur on a periodic basis throughout the study.

RCIGM will also perform a retrospective infant-only analysis on all subjects utilizing either an Artificial Intelligence platform or by performing a manual analysis similar to Athena at the end of the study.

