
The site PI/sub-I will speak with the physician of record and suitable subspecialists (for example, genetics, neurology, cardiology, etc.) at the time each test result is returned in order to review results and formulate a plan prior to returning a result to the parent/guardian.
 
The PI and/or sub-I at all sites are neonatologists or geneticists.
 
If the patient is discharged home prior to the return of results, the primary pediatrician should be contacted along with hospital clinical and research personnel.
	
Results will be disclosed to the family with as many members of the clinical team caring for the patient present as possible. At a minimum, each site will include one or more of the following: attending clinical geneticist, attending physician of record, attending neonatologist or geneticist who is a member of the study team. Additional attending subspecialists relevant to the particular genetic condition and genetic counselors may also participate in providing results to families. If clinical practice at a particular site is for licensed genetic counselors to return results without an attending physician as described above, the licensed genetic counselor may do so.
	
Recommendations to the family about changes in management or further genetic testing will be addressed by the physician of record as well as clinical genetics and other subspecialties per standard-of-care.
 
If a genetic problem exists that can be treated but does not need to be treated in the neonatal period, a referral to outpatient clinical genetics will be made.
	
It is strongly recommended that positive results or a VUS be disclosed in-person followed by a referral to a clinical geneticist. Depending on the need for timely action based on the results, it may be appropriate to return the result at the time of the next outpatient clinical genetics or related subspecialist appointment or to ask the family to come into the site to meet with the site PI to hear about the study results.
 
Under extraordinary circumstances (where the family lives hours away and/or has moved out of state), diagnostic or VUS results may be given by phone along with a clinical genetics referral. It is acceptable to convey negative/no finding results by phone with an offer for follow up genetic counseling visit.

Communication with a Biological Parent about a Parent Secondary Finding

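### Enrolling-site geneticists have a stated role in classifying rWGS variants but none for NewbornDx, and nothing keeps them from knowing the NewbornDx result first

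*Combined protocol and SAP*

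**What the plan says.** **rWGS classification.** In section 6.1.1, the RCIGM-CGC paragraph on pathogenicity reads: "The laboratory directors as well as Medical Geneticists and Genetic Counselors at RCIGM and at each site will assess pathogenicity of variants". The preceding paragraph on data analysis puts sign-out in the laboratory: "One of the analysts will then compile a report to be reviewed and reported by an ABMGG board-certified laboratory director".

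**NewbornDx classification.** Section 6.1.1, Athena (Quest) Variant Pathogenicity Determination: "Evidence is reviewed and assessed by a genomic variant scientist using a standard operation procedure", and then "The proposed pathogenicity classifications derived from the data are reviewed and approved by a board-certified laboratory director". The causality paragraph adds a report team of variant scientists, genetic counselors and a director. No enrolling-site role is stated.

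**Blind.** Section 6.1.1, opening paragraph: "The Athena (Quest) and RCIGM laboratories will be blinded to each other's result until all final results are returned". Site staff are not mentioned.

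**Flow of results to sites.** Under section 8.2, provisional results are telephoned to the attending physician and the site PI, and each final report is emailed to the site research team. The site PI or sub-investigator then confers with the physician of record and "suitable subspecialists (for example, genetics, neurology, cardiology, etc.) at the time each test result is returned".

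**What the classification decides.** The definitions at the front of the protocol make a positive result one classified pathogenic or likely pathogenic (P/LP). Section 9.4.2 takes a confirmed positive by each test as a primary endpoint. Section 9.4.1 adds the two discordant proportions and a confidence interval for the NewbornDx/rWGS ratio.

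**The concern.** This is a paired comparison: every infant has both tests, and the difference in calls is meant to reflect the platforms and their laboratories. That requires the two reads to follow comparable rules and neither to be informed by the other.

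The text leaves two gaps. First, an extra group of assessors contributes to one test only. Second, that group lies outside the blind and may already hold the other test's answer. Either gap could move a variant across the line between P/LP and variant of unknown significance (VUS) for rWGS without a matching step for NewbornDx. At stake are the rWGS yield, the discordant proportions and the ratio that bears on Hypothesis #1 in section 4.1 (NewbornDx finding at least 60% of rWGS diagnoses).

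**Working it through.** No figure in the plan is in dispute. The check compares the relevant texts and then follows the consequence through the planned estimates.

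**1. Is the site role unequal?** Yes, on the text. For rWGS, 6.1.1 names laboratory directors plus geneticists and genetic counselors at the laboratory and at each site. For NewbornDx it names a variant scientist and a laboratory director, with a laboratory team reviewing the report. Elsewhere in 6.1.1 (phenotype extraction, item 1) the same term for sites means the enrolling sites.

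**2. Are those site staff covered by the blind?** No. The blind names the two laboratories. The one specific safeguard, under phenotype extraction, stops Athena seeing rWGS results through the data-sharing route. Nothing equivalent stops a NewbornDx result held by the site from informing the rWGS read.

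**3. Can they know the NewbornDx result in time?** They can. Section 8.2 sends each laboratory's result to the site when issued and has it reviewed on return; genetics is one of the listed examples of who is consulted. Site PIs and sub-investigators are themselves neonatologists or geneticists. The instruction to wait for both results governs talking to the parents. It does not hold a result back from site staff, and it presupposes that a site may hold one result while the other is pending.

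**4. Does confirmation testing correct it?** No. The methods listed in 6.1.1 (MLPA, microarray, Sanger, qPCR) check that the variant is present. A suspicious VUS is also confirmed and still does not count as positive, so confirmation and classification are separate steps. Section 6.1.1 itself lists differing classification of the same variant as a cause of discordance.

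**5. Which estimates move?** Cross-classify the *n* infants in the modified intention-to-treat dataset: *a* positive on both tests, *b* NewbornDx only, *c* rWGS only, *e* neither.

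- NewbornDx yield = (*a* + *b*)/*n*
- rWGS yield = (*a* + *c*)/*n*
- Ratio = (*a* + *b*)/(*a* + *c*)

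Suppose site input changes the rWGS call in a net *k* infants (*k* > 0 for upgrades, *k* < 0 for downgrades).

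- Extra site judgement where NewbornDx is negative moves infants between *e* and *c*.
- Knowledge of a NewbornDx positive could move infants from *b* to *a*. Knowledge of a NewbornDx negative could move them from *c* to *e*.

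In every case *a* + *b* is unchanged, the rWGS yield becomes (*a* + *c* + *k*)/*n*, and the ratio becomes (*a* + *b*)/(*a* + *c* + *k*). So the rWGS yield, at least one discordant proportion and the ratio shift, while the NewbornDx yield does not.

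**6. Can *k* be derived?** No. The documents do not say how often site input changes a call, in which direction, or whose view prevails. The only NewbornDx turnaround given is a preliminary average of 13 days (section 2.2), and no study rWGS turnaround is stated, so how often NewbornDx comes first is also unknown. *k* could be zero.

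**The case against.** The strongest reply is that several tempting readings go beyond the text, and most of that reply stands.

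- **A reader might infer that the stated blind is broken.** The documents do not support this. The blind is between laboratories. A breach would need NewbornDx to report before rWGS classification is finished, the same site person to see it, and the rWGS call to change as a result. None of this is written into the plan; it is possible and unguarded.
- **A reader might infer that rWGS gets clinical information that NewbornDx lacks.** It does not. Both laboratories receive the same phenotype terms and records, and both use clinical presentation and family history for causality. The unequal element is site judgement on pathogenicity.
- **A reader might see a second leak where a laboratory queries the phenotype**, since "the additional or revised HPO terms needs to be redirected to the site for upload to the portal". That rule equalises information between the laboratories, and what passes is phenotype, not a test result.
- **A reader might infer that rWGS yield is inflated by some amount.** The documents give neither a rate nor a sign, and site review could equally downgrade variants.
- **A reader might single out the enrolling hospital that shares a name with the rWGS laboratory.** The documents do not state an affiliation, so excluding that site is not justified on this evidence.

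There are also real controls. A laboratory director reports the rWGS result. When discordance is due to classification, each laboratory documents its evidence, and steering-committee geneticists independent of the laboratories give a view (section 3 and section 8.2, Adjudication of Discordant Results). The Manual of Procedures, not among the documents, may add safeguards.

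These controls do not remove the point. Director sign-out does not take site input out of the call. The committee's view is an additional endpoint and does not replace the primary one. Independence is required only from the laboratories, so a site geneticist who helped classify the variant is not excluded from reviewing it.

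**Conclusion.** The concern holds in a limited form. As written, enrolling-site geneticists and counselors contribute to classification for one of two paired tests, outside the laboratory blind, at sites that receive the other test's result as issued. The primary yields and their ratio are therefore not protected as equally and independently read. The documents do not show that leakage occurs or that either yield is biased, and no size or direction can be given.

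This rests on reading the rWGS sentence literally and on the Manual of Procedures adding no safeguard. If the sentence does not describe actual practice, correcting it resolves the matter. The plan is descriptive, with no hypothesis test (section 9.1), so no formal decision turns on it. It should be fixed because the remedy is cheap and the affected quantities are primary; it is not a defect that invalidates the design.

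**What to change.** 1. **Section 6.1.1, RCIGM-CGC Variant Pathogenicity Determination.** Delete 'and at each site' for the classification counted in the rWGS primary endpoint. Alternatively, require that anyone contributing to it has not seen that infant's NewbornDx result. Deletion is better: blinding closes the leak but leaves the unequal site judgement.
2. **Role of sites.** State that sites supply phenotype to both laboratories, and that their view of discordant results is captured afterwards, as section 8.2 already provides.
3. **Infants already classified.** Flag those whose rWGS classification had site input, and report the yields and ratio with and without them. The laboratories already send the date and time of each preliminary result (data list in the Schedule of Activities). Use these to identify infants in whom NewbornDx came first. This shows order only, not whether the site person had seen the report.
4. **Sections 3 and 8.2, adjudication.** Extend the independence rule so that a site geneticist who took part in classifying an infant's variant does not review that infant's discordance.

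The cost is a short change to the protocol and Manual of Procedures, one flag in the laboratory transfer file and one sensitivity table. The small downside is that RCIGM loses site advice on pathogenicity before sign-out.
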